2.3. Exploratory Objective

1. To determine whether it is possible that use of GC will result in an overall reduced net cost to the healthcare system by avoiding treatment in many patients.

3. Study Design

This is a 4-5 year (up to 2 years enrollment , 3-year follow-up) prospective, cluster-crossover, unblinded, study of 550 subjects from at least fourteen centers of the Michigan Urological Surgery Improvement Collaborative (MUSIC), a physician-led quality improvement consortium comprised of the vast majority of urology practices within the state of Michigan.

According to the cluster-crossover design, each participating MUSIC clinical center within MUSIC will be randomized to either a Genomic Classifier care-based (GC) or Usual-Care-based (UC) strategy for a period of 3 months, during which all enrolled subjects within the center will be provided the assigned strategy. Random assignments will be generated centrally by a study statistician and provided to centers immediately before commencing enrollment in each 3-month period. The randomization will be based on a random block size of either 2 or 4. This will ensure that each center will have two periods of GC and two periods of UC during the enrollment period, maintaining study-wide balance and blinding of assignments in subsequent periods.

If enrolled during the GC period, both subjects and their treating physician will be provided GC (from GenomeDx) and CAPRA-S (from MUSIC-Central) to inform their treatment plan. In the UC periods, only the CAPRA-S results, provided by MUSIC-Central, will be available. Blinding of subjects and treating physicians will not be possible given the nature of the information.

Subjects enrolled to the GC arm will receive MUSIC-led education about the GC test. The pros and cons of the GC test need to be described by an unbiased clinician scientist including the past history of the test (published studies).

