7.1. Statistical Methods Supporting the Primary Objective

The Primary Objective of this study is to determine the impact of GC test result on adjuvant treatment decisions compared to clinical factors alone. This will be evaluated by testing for an effect of GC score in a regression model which adjusts for CAPRA-S risk score. As a cluster-crossover trial, a generalized linear mixed effects model will be used to model the probability of a subject receiving adjuvant treatment within center, in a specific period of the study. Since GC score is a subject-level covariate, an individual-level regression model is utilized rather than a cluster-level aggregated analysis (Campbell 2014, Chapter 6). Specifically, the model to be fit is

$$\text{logit}\left(\frac{\pi_{ijk}}{1-\pi_{ijk}}\right) = \beta_0 + \beta_1 G_i + \beta_2 (G_i * GC_i) + \beta_3 \text{CAPRA-S}_i + \gamma_j + \phi_k$$

where π_{ijk} is the probability of treatment for the i^{th} subject enrolled in the j^{th} cluster (ie: center) during the k^{th} period, G_i is the group to which the subject is enrolled (GC=1, UC=0), CAPRA-S_{*i*} is that subjects' CAPRA-S score (0-12), GC_{*i*} is the GC score (0-1), $\beta_0 \sim N(\mu, \sigma^2)$ and

$\phi_k \sim N(0, \sigma^2)$ are random cluster and period effects, respectively. The null hypothesis $\beta_2 = 0$ will be tested using a Type III test (SAS PROC GLIMMIX) at a 0.05 significance level. 95% confidence intervals using robust variance estimates will also be calculated.

In addition to the model described above, an additional model including a group-by-period interaction term will be fit to ensure that group assignment in a period is not effected by preceding or subsequent periods. For the purposes of this analysis, the period effect will be

considered fixed. This may detect carry-over effects if behaviors or attitudes of physicians within sites persist or change over the course of the study or if changes in patient education materials or their presentation change from one period to the next. Should this interaction term be significant, an alternative analysis utilizing non-consecutive periods may be used.

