7.5. Simulation settings

In order to determine plausible values of the parameters of the model described in Section 7.1, several clinical utility studies of the GC were pooled and utilized in a re-sampling routine to determine likely values of parameters for the current study. Although none of the previous clinical utility studies were randomized comparative trials, the DECIDE (Badani 2013), ASSESS-D (Badani 2014), and PRO-ACT Michalopolous (2014) studies did involve real high-risk patient cases (only those that were pT3 or SM+ are included here) from community and tertiary care facilities and can be expected to provide similar clinical and genomic characteristics to those eligible for this trial. In all studies, treatment recommendations were provided by physicians initially without GC risk scores then (in a blinded fashion) with knowledge of both clinical and GC risk.

There are a total of 530 recommendations with and without GC available from these clinical utility studies. To approximate a parallel-group (GC and UC) randomized trial, for each run of the re-sampling routine, the data was randomly halved, taking half of the recommendations made with knowledge of the GC ($n = 265$) and the other half with recommendations made without knowledge of the GC ($n = 265$). Ten-thousand such data sets were generated and to each, a generalized linear model of the probability of treatment was fit, similar to that described in Section 7.1 but involving only the fixed effects. Across these 10,000 samples, the mean ORs of GC score, CAPRA-S score, and arm (GC vs UC) are, respectively, 1.47, 1.15, and 0.24. The overall rate of adjuvant treatment of CAPRA-S high-risk patients in MUSIC clinics is ~8%.

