7.5.1 Power and Sample Size Simulation

Generating CAPRA-S and GC Scores

Simulation was used to determine the sample size necessary to have adequate power to reject the null hypothesis, $H_0: \beta_2 = 0$, based on the model in Section 7.1. CAPRA-S and GC risk scores for the simulated datasets were based on the distributions observed in the PRO-ACT clinical utility study (Michalopolous 2014). The distribution of CAPRA-S risk in PRO-ACT clinical is similar to that of MUSIC (62.7% vs 55.8% low risk and 44.2% vs 37.3% high risk). The distribution of GC risk scores among MUSIC patients is unknown, but due to the similarity in CAPRA-S scores, it is assumed that it will also be somewhat similar to PRO-ACT.

To ensure a) the GC score distribution is comparable to PRO-ACT, b) the CAPRA-S risk distribution is as similar as possible to MUSIC, c) the true variability of the continuous GC score, and d) the underlying correlation between GC and CAPRA-S risk is maintained, the following procedure was used to generate GC and CAPRA-S scores for each simulated individual:

1. A random percentile is generated (0-100%) and rounded to the nearest 5%.
2. PRO-ACT scores with GC score (and corresponding CAPRA-S score) within that percentile range (eg: 20-25th percentile) are then selected.
3. A GC score is then generated as a uniform a random number between the maximum and minimum of the selected PRO-ACT GC scores.
4. An initial CAPRA-S score is then randomly sampled from the selected CAPRA-S scores. The initial CAPRA-S score is then incremented by 1-point (to a maximum of 12) with 75% probability to up-adjust the slightly lower risk in PRO-ACT.

Generating Enrollments

Based on data available from MUSIC-central, the peak performing clinical centers exceeded 10 radical prostatectomy cases per month, with case-loads below 5 per month for the 4th and 5^h centers. Enrollments per site*month were generated using a Poisson process using the following conservative means: Site 1: 10, Site 2: 10, Site 3: 5, Site 4: 5, Site 6-8: 4, Site 9 and higher: 2.

Sites were randomized to enroll subjects to the GC or UC arm for each period using a fixed-block size enrollment (2, 3, or 4 depending on the randomization ratio of the simulation). Period length varied from month to year.

Intra-Class Correlations

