7.5.2 Simulation Results

Partial simulation results are listed in Table 1. Five-thousand simulated datasets were generated and analyzed at each setting – simulation error is ~ 0.5%. Various combinations of the site-ICC, number of sites, duration of randomization periods, and sample size were attempted. A study of 350 subjects at 14 clusters (centers) enrolled over 3-month periods equally randomized to GC or UC, will have 83% power to detect a significant CAPRA-S-adjusted effect of GC score on the likelihood of adjuvant therapy at the 0.05 level. Such a study will require 8-12 months (ie: 3-4 periods) for recruitment.

Minor perturbations in the ICC (15-35%), number of sites (5-10), and the randomization period duration (1-4 months) did not effect the power by more than 1%, with a sample size of 350. However, including 4 or fewer sites will result in a power < 80% and while inclusion of 8 or

more sites will maintain the desired power (> 80%), inclusion of these lower-recruiting sites will not appreciably decrease the enrollment period.

Additional components influencing the required sample size are the total event rate, average and variance of site-period recruitment, and actual approximation of the randomization ratio (will not be exactly 1:1). These, as well as the site-ICC, will be evaluated as described in Section 7.2, Sample Size Re-Estimation.

Table 1: Power comparisons for various sample sizes.

Site-ICC	Number of Sites	Period Duration (months)	Approx. Duration of Enrollment (months)	Sample Size	Power
23%	8	3	6	200	47%
23%	8	3	6	250	60%
23%	8	3	7	300	77%
23%	8	3	8	350	83%
23%	8	3	9	400	88%
23%	8	3	12	500	93%

8. Confidentiality and Ethical Issues

The Principal Investigators are responsible for conducting this Study Protocol. The study will be reviewed and approved by an IRB/EC and appropriate Scientific Review Committees prior to initiation.

All participating physicians must sign a confidentiality and non-disclosure agreement.

9. Scientific Presentation and Publication Policy

Presentation and publication of the results will be based upon appropriate analysis and review of the complete data, and the usual rules for determining authorship will guide scientific presentation and publication of the results of this study. Written approval from GenomeDx Biosciences is required prior to disclosing any confidential information relative to this study.

10. Data and Safety Monitoring

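### Section 7.1 promises a robust-variance 95% CI for the primary effect but names no small-sample correction, degrees of freedom or clustering unit; with about 14 centres, a standard uncorrected version covers mostly 86–91%

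*Combined protocol and SAP*

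**What the plan says.** Section 7.1 fits a logistic mixed model with random centre and period effects. The null hypothesis beta2 = 0 "will be tested using a Type III test (SAS PROC GLIMMIX) at a 0.05 significance level". The next sentence gives the interval: "95% confidence intervals using robust variance estimates will also be calculated". Only the interval is called robust. Neither Section 7.1 nor any other section states a small-sample correction, the degrees of freedom, the unit over which the robust variance is summed, or what happens if interval and test point in different directions.

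Section 3 (Study Design) describes a "study of 550 subjects from at least fourteen centers", in which "each center will have two periods of GC and two periods of UC during the enrollment period". Section 7.5.2 bases its power statement on a smaller trial: "A study of 350 subjects at 14 clusters (centers) enrolled over 3-month periods equally randomized to GC or UC, will have 83% power". Section 7.5.1 plans for centres of very different size, with monthly means "Site 1: 10, Site 2: 10, Site 3: 5, Site 4: 5, Site 6-8: 4, Site 9 and higher: 2".

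**The concern.** A sandwich variance is estimated from the spread of cluster-level score contributions, so its accuracy depends on the number of independent clusters. In its uncorrected form it tends to be too small when clusters are few, and a normal critical value ignores how imprecisely it is estimated. Fourteen centres is few. The information on beta2 also comes only from the GC arm, because the term is the product of arm and GC score.

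Two things are at stake. The only interval the plan names for its primary effect may be too narrow to be called 95%. And the plan leaves open which variance drives the test. If it differs from the interval's, the two can contradict each other on the primary hypothesis. If it is the same uncorrected sandwich, the test itself over-rejects.

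**Working it through.** **Inputs from the plan.** N = 550 and at least 14 centres (Section 3); N = 350 (Section 7.5.2); four periods per centre (Section 3); monthly enrolment means (Section 7.5.1); odds ratios, for which Section 7.5 says "the mean ORs of GC score, CAPRA-S score, and arm (GC vs UC) are, respectively, 1.47, 1.15, and 0.24"; centre ICC 23% and period ICC 3% (Section 7.5.1).

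**Inputs assumed because the plan does not give them.** GC score ~ Beta(1.9, 2.6), correlated 0.35 with CAPRA-S; mean CAPRA-S about 4; OR 1.47 read as per 0.1 of GC score; site 5, missing from the enrolment list, set to 4.5 per month; intercept varied, because the roughly 8% treatment rate in Section 7.5 is for CAPRA-S high-risk patients only.

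**Check of the ICC.** With centre variance 1 on the logit scale, 1/(1 + π²/3) = 1/4.29 = 23.3%, matching the stated 23%. A period variance of 0.13 gives 0.13/(0.13 + 1 + 3.29) = 2.9%, matching 3%.

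**The plan's own power figure.** Simulated power of the model-based test at N = 350 with 8 sites is 77%, 80%, 83% and 85% at overall treatment rates of 8.6%, 10.3%, 11.0% and 11.6%. With 14 sites it is 81–84%. The stated 83% lies within these ranges, but only by choice of intercept, so this is a plausibility check and not a reproduction. At the intercept giving 80%, N = 200 gives 58% (Table 1: 47%) and N = 500 gives 92% (Table 1: 93%). The text ties 83% to 14 centres, whereas Table 1 lists 8 sites for that row.

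**Estimators.** Let A be the model-based information matrix and U_j the score contribution of centre j.
- Model-based: Var = A⁻¹.
- Uncorrected sandwich: Var = A⁻¹ (Σ_j U_j U_jᵀ) A⁻¹, with interval b ± 1.96·SE.
- Corrected: the same form, with residuals inflated for leverage (Mancl-DeRouen) and a t critical value on 14 − 1 = 13 df.

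**Results.** 14 unequal centres, 1,000–1,500 simulated trials per row, Monte Carlo error about 1 point; all figures in %. "Disagree" compares the model-based test with the uncorrected robust interval.

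| Setting | Treated | Robust CI coverage | Model-based CI coverage | Robust CI excludes 0 | Model-based test rejects | Disagree | Corrected CI coverage |
|---|---|---|---|---|---|---|---|
| N=350, planning effect | 10.3 | 86.7 | 95.9 | 85.3 | 81.3 | 9.6 | 94.3 |
| N=350, planning effect | 11.2 | 90.7 | 96.1 | 85.9 | 84.1 | 10.0 | 95.3 |
| N=350, null | 9.2 | 87.1 | 95.1 | 12.9 | 4.9 | 8.7 | 93.3 |
| N=550, planning effect | 10.4 | 88.3 | 95.0 | 95.1 | 94.5 | 3.4 | 94.8 |
| N=550, planning effect | 8.9 | 89.6 | 95.9 | 93.7 | 92.4 | 3.5 | 95.5 |
| N=550, planning effect | 5.9 | 86.7 | 94.6 | 84.7 | 81.2 | 10.1 | 93.1 |
| N=550, half the effect | 9.1 | 89.0 | 94.9 | 51.5 | 43.6 | 15.3 | 94.6 |
| N=550, null | 7.4 | 86.6 | 95.3 | 13.4 | 4.7 | 10.0 | 93.2 |
| N=550, null | 9.3 | 90.8 | 96.5 | 9.2 | 3.5 | 6.7 | 95.8 |
| N=550, null | 19.7 | 91.1 | 95.6 | 8.9 | 4.4 | 6.3 | 96.6 |

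Further runs with other assumed inputs widen uncorrected centre-clustered coverage to 83–92%, and the null rejection rate to about 17%. Clustering by centre-period (14 × 4 = 56 units) gives 86–94%.

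**Cause.** The assumed monthly means sum to 58.5 and their squares to 342.25, so the effective number of equal centres is 58.5²/342.25 = 10. Even so, at N = 550 with the planning effect, making centres equal in size raises coverage only from 88.3% to 90.0%. Doubling to 28 centres raises it to 91.5%. At N = 350 and a common intercept, going from 8 to 14 centres raises it from 85.1% to 90.7%. The number of centres matters more than their imbalance.

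**Which part of the correction is needed.** At 14 centres, t on 13 df without the bias correction covers 90–94%. The bias correction with 1.96 covers 91–94%. Both together cover 93–97%.

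**The case against.** The strongest reply is that the plan is silent rather than wrong. It does not say the sandwich is uncorrected, that 1.96 is the multiplier, that clustering is by centre, or that the Type III test is model-based. That stands: a reader might infer that the error bars are wrong as written, and the text does not support this. It supports only that the choices are unspecified and that the most natural reading of the sentence gives an interval below 95%.

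Second, the primary decision rests on the test and the interval is additional. That also stands. If the test is model-based it rejected in 3.5–5% of null trials, so the primary conclusion is not shown to be at risk on that reading.

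Third, a reader might infer from the N = 350 rows that test and interval would conflict in about one trial in ten. For the planned 550 subjects, the planning effect and 9–10% treated, the figure is 3–4%. Larger figures need fewer events, a smaller or null effect, or 350 subjects.

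Fourth, centre-period is the unit of assignment, and clustering there narrows the gap. True, but 86–94% is still mostly short of 95%, and the plan does not choose that unit.

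Fifth, a robust interval protects against misspecification. When the GC slope varied by centre, model-based coverage did fall to 91.9%. But the uncorrected robust interval covered 87.9% in the same setting, so it did not deliver that protection; the corrected one covered 93.9%.

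**Conclusion.** The concern holds as a specification gap with a measurable consequence. As most naturally read, Section 7.1 yields a nominal 95% interval that covers mostly 86–91% when clustered by centre (83–92% over all runs), against 95–97% for the model-based interval under a correctly specified model. The silence about the test does not remove the problem. Either the test uses a different variance, and disagreement runs from about 3% to 15% of trials depending on N, event rate and true effect, or it uses the same uncorrected variance and type I error is about 9–17%. Only a small-sample correction that the plan does not state would avoid both.

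The findings do not show that the primary test is invalid, nor that unequal centre sizes are the main cause. The exact percentages depend on the assumed GC distribution, OR unit and intercept, but centre-clustered under-coverage appeared in every scenario run. The point should be settled before analysis; it does not undermine the design.

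**What to change.** State in Section 7.1 one variance estimator for both the Type III test and the 95% CI, with its clustering unit and degrees of freedom. Either of these would do:

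- **Model-based for both.** Take the interval from the covariance and degrees of freedom of the Type III test. The cost is no protection if the model is misspecified, for example if the GC slope differs between centres (about 92% coverage).
- **Corrected robust for both.** Use a bias-corrected sandwich clustered by centre, with t on centres minus 1 df. Both parts are needed. The Mancl-DeRouen form was the one checked here, with 93–97% coverage; another correction should be simulated before it is adopted. The cost is a wider interval and slightly lower power, which can be measured by adding the estimator to the Section 7.5 simulation.

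Either change takes a sentence and a procedure option. Design, sample size and data collection are unchanged.

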7.2. Interim Sample Size Re-Estimation

A confirmation of assumptions underlying the model described in Section 7.1 and the Power and Sample Size calculations in Section 7.4 will be conducted after no fewer than 150 subjects have been enrolled and adjuvant treatment determinations have been made, several parameters will be estimated based on the accumulated data, but no hypothesis testing will be performed and Type I error will be nominally effected (Lake 2002). The following parameters will be estimated and compared to those assumed in Section 7.4, and the impact on the estimated sample size determined through simulation:

- average enrollment by center, including variance of enrollment and enrollment by period
- intra-cluster correlation (ICC)
- overall rate of treatment

Based on the estimated parameters, the number of centers or sample size may be adjusted while maintaining the requisite 80% power. If simulations indicate that a sample size increase of $>20\%$ will be required to provide adequate power to achieve the Primary Objective, the study may be terminated due to futility.

7.3. Statistical Methods Supporting the Secondary Objectives

All tests will be two sided at a 0.05 significance level. Individuals who are lost to follow-up will be considered censored in time to event analyses. Treatment plans available at the time of drop-out will be considered the final treatment plans.

Secondary Objective 1: To determine whether the net benefit to subjects in the GC arm is superior to the UC arm. This will be determined by directly calculating the net benefit (Vickers and Elkin 2006) across a range of treatment thresholds, Decision Curve Analysis (DCA). DCA is a method for assessing prognostic models that incorporates clinical consequences and the potential probability thresholds at which the likelihood of a given outcome (eg: progression to metastatic disease) may influence the treatment decision of a patient and their physician. For example, one individual may choose treatment if there is a 5% chance of a given outcome while another individual may not be influenced unless the likelihood of that outcome is as high as 10 or 15%. Thus, this methodology allows for how different patients may differentially weigh false negative or false positive results. The calculated net benefit is plotted against threshold

probabilities, and different prediction tools (eg. CAPRA-S and GC) can be compared across these probabilities. If GC is not superior to UC across all thresholds, the region of superiority will be evaluated to determine if it contains a clinically meaningful ratio of harm due to unnecessary treatment versus missed treatment.

Secondary Objective 2: To determine whether use of the GC test result results in decreased likelihood of treatment for CAPRA-S high and increased likelihood of treatment for CAPRA-S low, a modeling approach similar to that of supporting the Primary Objective will be used, but with a GC-by-CAPRA-S interaction term as follows:

$$\text{logit}\left(\frac{\pi_{ijk}}{1-\pi_{ijk}}\right) = \beta_0 + \beta_1 G_i + \beta_2 (G_i * GC_i) + \beta_3 CAPRA-S_i + \beta_4 (G_i * CAPRA_i * GC_i) + \gamma_j + \phi_k$$

where parameters are defined as previously. The test of $H_0: \beta_4 = 0$ will be performed using a Type III test (SAS PROC GLIMMIX). The direction of the interaction will be evaluated graphically with the probability of treatment based on the model and for empirical probabilities using pre-defined GC and CAPRA-S cutoffs.

Secondary Objective 3: Time-to salvage therapy initiation will be modeled using a Cox formulation of a Frailty regression model with a similar formulation (ie: main and random effects) to that used for the primary analysis. Kaplan-Meier curves for GC and UC arms will be plotted, as well as for combinations of high- and low-risk GC and CAPRA-S groups.

Secondary Objective 4: Time-to BCR and metastatic progression will be evaluated similarly to the model described for Secondary Objective 3.

Secondary Objective 5: Summary statistics for all QOL instruments and corresponding confidence intervals will be calculated and compared for the GC and UC subjects and shown graphically over time. Validated instruments are used to measure erectile function, urinary function, sexual interest, and sexual satisfaction. Scores for each domain will be scaled with a minimum to maximum range of 0-100. Comparisons between GC and UC subjects will be made at each timepoint (3, 6, 12 and 24 months after surgery) and on each domain and overall score (VAS 0-10), using an ANCOVA analysis including adjustment for time since surgery. Should the assumptions for ANCOVA not be met (strongly skewed data or substantial ceiling or floor effect) a semiparametric ANCOVA model will be used (as in Buja 1989) to adjust for time-from surgery. If the distribution of time-from surgery is similar in the two groups, a Mann-Whitney test for differences will be used to corroborate the ANCOVA model. For this secondary objective, there will be no adjustment for multiple comparisons across domains or time points.

Exploratory Objective: Using a variety of budget models the cost of care for patients in the GC vs. UC arms will be compared out to 3 years from surgery. This will include estimated costs for adjuvant therapy. Differences in total cost, and differential cost per patient (UC vs GC) will be calculated and compared using either standard t-tests if data is normally distributed or appropriate non-parametric test if data is right skewed.

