One such assay is Decipher from GenomeDx Biosciences, a GC assay developed and validated in a post-RP setting as a predictor of eventual metastasis (Erho 2013). Studies have demonstrated independent prognostic value of this GC assay above and beyond standard clinicopathologic parameters reclassifying the clinically high-risk men tested into lower or significantly elevated risk of metastatic disease progression (Karnes 2013, Den 2014, Cooperberg 2015, Klein 2015, Den 2015, Ross 2015, Yamoah 2015). Studies have demonstrated that Decipher low risk patients can safely delay/defer treatment and avoid the adverse side effects of radiation treatment after radical prostatectomy while Decipher high risk patients can benefit from early adjuvant radiation (Den 2014, Den 2015).

In addition to clinical validation, several decision impact studies of Decipher were conducted to investigate a GC's influence on physicians' post-radical prostatectomy treatment recommendations (Badani 2013, Badani 2014, Michalopoulos 2014, Nguyen 2015).

Badani (2013) evaluated the influence on urologist treatment recommendations with GC in comparison to clinicopathologic risk factors alone for patients from a tertiary care center. This prospective, pre-post design study showed that among twenty-one high volume (i.e., mean 180 RP/year) urologic surgeons from 18 US institutions who were asked to make treatment recommendations for 24 prostate cancer patient cases post-RP, 43% changed their treatment recommendation with the addition of genomic information to standard clinicopathologic information.

To further reflect the distribution of test results and risk of metastasis among high-risk patients seen in a broader range of clinical settings other than academic centers, a prospective, multi-center, decision-impact study (ASSESS-D, Badani 2014) evaluated the effect of knowledge of the GC model on urologist treatment decision-making in a population of patients having undergone radical prostatectomy in a community-based practice. One hundred ten patient case histories were available for review by 51 urologists. Overall, 31% (95% CI: 27- 35%) of treatment recommendations changed with knowledge of GC. Treatment intensity was strongly correlated with the GC-predicted probability of metastasis ($p < 0.001$) and the GC was the dominant risk factor driving decisions in multivariable analysis (OR=8.6, 95% CI: 5.3-14.3%, $p < 0.0001$).

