2.2. Secondary Objectives

1. To determine whether the decision impact of the GC test is of benefit to patients. Specifically, is net benefit of GC use superior to those who do not have the GC test as assessed by decision curve analysis.
2. To determine whether use of the GC test results in decreased likelihood of adjuvant treatment for subjects with high CAPRA-S score (≥ 5) and increased adjuvant treatment for subjects with low CAPRA-S score (< 5). The hypothesis is that there is a non-zero interaction between GC test use and CAPRA-S.
3. To determine whether GC use is associated with earlier use of salvage therapies in CAPRA-S low risk patients and later use of salvage therapy in CAPRA-S high-risk patients.

4. To determine whether use of GC results in improved protection from BCR and metastatic progression.
5. To investigate the impact of GC use on QOL, and whether there is differential QOL impact among CAPRA-S high- and low-risk patients.
6. To determine whether collaborative-wide education and the use of CAPRA-S scores in the control group impacts rates of adjuvant radiotherapy compared to historical controls.

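### Secondary Objective 1 asks whether GC-driven decisions benefit patients, but the only calculation described is a decision curve on prognostic tools, which does not take treatment received as an input

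*Combined protocol and SAP*

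**What the plan says.** Section 2.2 states the first secondary objective as "To determine whether the decision impact of the GC test is of benefit to patients" and makes it specific: "is net benefit of GC use superior to those who do not have the GC test as assessed by decision curve analysis". Section 7.3 restates it as a contrast of randomised strategies: "To determine whether the net benefit to subjects in the GC arm is superior to the UC arm".

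Section 7.3 then describes the method. Net benefit is calculated over a range of treatment thresholds. "DCA is a method for assessing prognostic models that incorporates clinical consequences", and "different prediction tools (eg. CAPRA-S and GC) can be compared across these probabilities". The outcome appears only as an example: "likelihood of a given outcome (eg: progression to metastatic disease". Treatment appears as something that the threshold "may influence the treatment decision of a patient and their physician", not as a data item in the calculation. If GC does not win at every threshold, the thresholds where it does win are reviewed for an acceptable balance between needless and missed treatment.

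The section does not define a true or false positive, does not say how an arm-level net benefit is formed, and fixes neither outcome nor threshold range. Adjuvant treatment received is the primary endpoint (Section 5.1), and 3-year BCR and metastasis are secondary endpoints (Section 5.2).

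**The concern.** The objective is about decisions, so its answer should depend on what was decided. A standard decision curve does not. It scores each man by whether his predicted risk exceeds a threshold, as if every man above it were treated and every man below it were not. It asks whether GC predicts better than CAPRA-S. Section 1 already presents "independent prognostic value of this GC assay above and beyond standard clinicopathologic parameters" as demonstrated, and answering that question needs no randomised arms: Section 6.1 collects tissue in both arms, so both tools could be scored in the same men.

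At stake is the reading of the one analysis that sets treatment burden against events. Section 1 says that the clinical utility of GC still lacks confirmation in a randomised trial. A prognostic result reported under Objective 1 could be taken as that confirmation. Equally, if GC predicts well but changes decisions badly, the curve would not show it.

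**Working it through.** The plan gives no event rate, power or net-benefit figure for this objective, so there is nothing to reproduce. Three checks follow. The first needs no data assumption; the others are illustrations.

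**1. The formula.** At threshold t, NB(t) = TP/n - (FP/n) x t/(1-t). For a prediction tool, TP counts men with predicted risk at or above t who have the event, and FP those at or above t who do not. The inputs are predicted risk, t and outcome. Treatment received is absent. It can enter only by altering the outcome, and then an event prevented in a flagged man is scored as a false positive.

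**2. Does the curve respond to decisions?** Assumptions, none from the documents: 10% events; log-OR per SD of 0.5 for CAPRA-S and 1.0 for GC; correlation 0.4; treatment does not alter the outcome; 2,000,000 simulated men. Treatment is set at 8% per arm (Section 7.5 gives about 8%, but for CAPRA-S high-risk men). GC-minus-UC difference in net benefit at t = 10%:

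| Influence of GC on treatment in GC arm (log-OR per SD) | Positive call = tool risk at or above t | Positive call = treatment received |
|---|---|---|
| 0 (reports ignored) | 0.0104 | 0.0000 |
| 0.5 | 0.0104 | 0.0050 |
| 1.0 | 0.0104 | 0.0091 |
| 2.0 | 0.0104 | 0.0152 |

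The tool-based difference is the same whether reports are ignored or followed closely. It also depends on GC being the better predictor: with equal strength it is about 0, and with an uninformative GC it is at or below 0 apart from simulation noise.

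**3. How often would GC be favoured with no decision changed?** Assumptions: 20% events; 550/2 = 275 men per arm; outcome logit = a + 0.6 x CAPRA-S + b x GC on standardised scores; correlation 0.3; net benefit averaged over thresholds 5-30%; no clustering. Approximate percentages of simulated trials:

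| b (AUC, CAPRA-S to both) | Same men, both scores v CAPRA-S: mean > 0 | Same men: lower 95% limit > 0 | Cross-arm: mean > 0 | Cross-arm: lower limit > 0 | GC alone v CAPRA-S: mean > 0 |
|---|---|---|---|---|---|
| 0.3 (gain 0.015) | 79 | 12 | 53-57 | 3-4 | 16 |
| 0.6 (0.69 to 0.74) | 95 | 36 | 63 | 5 | 49 |
| 0.9 (0.70 to 0.78) | 99 | 66 | 75 | 9-11 | 84 |

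Cross-arm means both scores in GC men against CAPRA-S in UC men. The references are about 50% for a mean above 0 and 2.5% for a lower limit above 0. Repeat runs differ by a few points. The plan's literal requirement, superiority at every threshold, is met less often: about 21-55% in the same men for the two larger gains, and sensitive to threshold spacing. The fallback review of a favourable region cannot be quantified.

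**4. Is it enough to call treatment received the positive?** Not without a caveat. Suppose both arms treat 8%, and the GC arm treats a further proportion D of men who would have the event, in place of men who would not. If treatment prevents a fraction e of events, the difference at t = 10% is D x (1-e) x (1 + 1/9). With D = 0.0065 this gives 0.0072, 0.0036, 0.0014 and 0 for e = 0, 0.5, 0.8 and 1. Simulation gave 0.0071, 0.0035, 0.0015 and 0. Events averted, D x e, meanwhile rise from 0 to 0.0065. The measure falls as treatment works better.

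**The case against.** The strongest reply is that Section 7.3 does not commit to a comparison of predictors. CAPRA-S and GC are introduced with eg, as an illustration of what the method can do. The same paragraph sets GC arm against UC arm and judges the result on needless versus missed treatment. Those words fit a net benefit by arm with treatment received as the positive call. This stands in part. A reader might infer that the plan is fixed on ignoring treatment decisions; the documents do not support that. They support something narrower: the positive call is undefined, and the one calculation described does not match the objective. Labelling the contrast by arm does not cure this, because applying GC in one arm and CAPRA-S in the other still leaves decisions out.

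A reader might also infer that GC would almost always be declared superior. That holds only for both scores against CAPRA-S in the same men, on mean net benefit, with a material prognostic gain. The plan's stated contrast is between arms, where the lower limit clears 0 in only about 4-11% of trials.

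Third, utility would not simply pass as confirmed. The primary analysis (Section 7.1) tests whether GC score drives treatment received, so ignored reports should show there. Objectives 4 and 5 address BCR, metastasis and QOL by GC use. This limits the consequence.

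Finally, Section 2.2 itself names decision curve analysis, so insisting on one replacement formula would be a preference. That is accepted; the requirement is that treatment received and outcome enter by arm.

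**Conclusion.** The point holds as a mismatch between objective and described method, and should be corrected. That a tool-based decision curve takes no account of treatment received follows from its formula and rests on no assumption. That it can favour GC with no decision changed requires GC to add prognostic information, which Section 1 asserts.

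The size is uncertain. Under the third check's assumptions, GC is favoured in about 79-99% of trials in the same-men comparison (lower limit above 0 in 12-66%) but in about 57-75% across arms, with the low end at 53% in a repeat run. With GC alone against CAPRA-S, equal strength gives a coin toss. Event rates, AUCs and correlation are not in the documents, and clustering was not simulated. The primary analysis is unaffected.

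**What to change.** In Section 7.3, Secondary Objective 1:

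- Base the test on an arm-level net benefit, GC versus UC as randomised, using adjuvant treatment received and the observed 3-year outcome. One example is (event rate UC - event rate GC) - w x (adjuvant rate GC - adjuvant rate UC), where w is the event reduction judged worth one course of treatment. If no decision changes, both differences have expectation 0. With w = 0.10, for illustration only, its lower 95% limit exceeded 0 in 2.2-2.8% of simulated trials under that null, without clustering.
- Name the outcome and fix the range of weights or thresholds before outcome data are analysed.
- Give a 95% interval that respects center and center-period.
- If true and false positives are instead defined from treatment received, state that effective treatment biases the measure.
- Keep the CAPRA-S versus GC decision curve as a description of prognostic performance only.

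The cost is SAP text and one added analysis on endpoints already collected. The drawback is precision. At 20% events and 275 men per arm, the half-width for the event-rate difference alone is 1.96 x sqrt(2 x 0.2 x 0.8/275) = 0.067, or 6.7 percentage points, with no allowance for the clustered design. A positive claim becomes harder to reach.
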